## **5.17. Clinical Trial Registry Analyses**

Analyses provided for the Clinical Trial Registry requirements will include the following:

Summary of AEs, provided as a dataset which will be converted to an XML file. Both SAEs and ‘Other’ AEs are summarized: by treatment group, by MedDRA preferred term.

- An AE is considered ‘Serious’ whether or not it is a TEAE.
- An AE is considered in the ‘Other’ category if it is both a TEAE and is not serious. For each SAE and ‘Other’ AE, for each term and treatment group, the following are provided:
  - the number of participants at risk of an event
  - the number of participants who experienced each event term
  - the number of events experienced.
- Consistent with [www.ClinicalTrials.gov](http://www.ClinicalTrials.gov) requirements, ‘Other’ AEs that occur in fewer than 5% of subjects in every treatment group may not be included if a 5% threshold is chosen (5% is the minimum threshold).

## 6. Appendices

---

## Appendix 1. Potentially Clinically Significant ECGs

---

Parameter	Unit	Low PCS Criteria	High PCS Criteria
QRS Interval	msec	NA	$\geq 120$
PR Interval	msec	NA	$\geq 220$
QTcF	msec	NA	$> 500$
QTc interval: change from baseline		$> 60$ msec at any time after randomization	

---

Abbreviations: NA = not applicable; PCS = potentially clinically significant; QTc = corrected QT interval; QTcF = Fridericia's corrected QT interval.

## Appendix 2. Potentially Clinically Significant Laboratory Values

Parameter	Conventional Unit	Low PCS Criteria	High PCS Criteria	SI Unit	Low PCS Criteria	High PCS Criteria
Hematology (whole blood)						
Hemoglobin (male)	g/dL	<11	>18	g/L	110	180
Hemoglobin (female)	g/dL	<10	>17	g/L	100	170
Hematocrit	%	<30	>50 (F) >55 (M)	L/L	<0.3	>50 (F) >55 (M)
Leukocyte (WBC Count)	X 10  /uL	≤2.8	≥15	X 10  /L	≤2.8	≥15
Neutrophils	Cells/mm 	1500	NA	Proportion of 1.0	≤0.15	NA
Platelet Count	X 10  /uL	≤75	≥700	10  /L	≤75	≥700
Chemistry (serum or plasma)						
ALT (SGPT)	U/L	NA	≥3 X ULN	U/L	NA	≥3 X ULN
AST (SGOT)	U/L	NA	≥3 X ULN	U/L	NA	≥3 X ULN
Total Bilirubin	mg/dL	NA	≥1.5 X ULN	umol/L	NA	≥1.5 X ULN
BUN	mg/dL	NA	≥30	mmol/L	NA	≥10.71
Creatinine Kinase (CK)	U/L	NA	≥3 X ULN	U/L	NA	≥3 X ULN
Sodium	mEq/L	≤125	≥155	mmol/L	≤125	≥155
Potassium	mEq/L	≤3.0	≥5.5	mmol/L	≤3.0	≥5.5
Calcium	mg/dL	Corrected Value ≤7.5	Corrected value ≥12.0	mmol/L	≤1.875	≥3
Alkaline Phosphatase	U/L	NA	≥3 X ULN	U/L	NA	≥3 X ULN
Albumin	g/dL	≤2.6	≥6.0	g/L	≤26	≥60

Parameter	Conventional Unit	Low PCS Criteria	High PCS Criteria	SI Unit	Low PCS Criteria	High PCS Criteria
Chloride	mEq/L	≤85	≥120	mmol/L	≤85	≥120
Glucose (random)	mg/dL	≤45.1	≥200.0	mmol/L	≤2.48	≥11
Serum Creatinine	mg/dL	NA	>1.5 X ULN	umol/L	NA	>1.5 X ULN
Gamma-Glutamyl Transferase (GGT)	U/L	NA	≥3 X ULN	U/L	NA	≥3 X ULN
TSH	uU/L	below normal range	above normal range	mIU/L	below normal range	above normal range
Urinalysis						
Hb/RBCs/Blood					NA	≥ + 2
Protein/Albumin					NA	≥ + 2
Glucose					NA	≥ + 2

Abbreviations: ALT = alanine aminotransferase; AST = aspartate aminotransferase; F = female; Hb = hemoglobin; M = male; NA = not applicable; PCS = potentially clinically significant; RBCs = red blood cells; SGOT = serum glutamic oxaloacetic transaminase; SGPT = serum glutamic pyruvic transaminase; SI = Système International; TSH = thyroid-stimulating hormone; ULN = upper limit of normal; WBC = white blood cell.

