9.4.6. Safety Monitoring

Lilly will periodically review evolving aggregate safety data within the study by appropriate methods. An AC will be designated for at least one interim evaluation of unblinded safety data from Study LLCF (Section 10.3.7).

If a study patient experiences elevated ALT \geq 3X ULN, ALP \geq 2X ULN, or elevated TBL \geq 2X ULN, hepatic laboratory tests (Appendix 4) must be repeated within 3 to 5 days including ALT, AST, ALP, TBL, direct bilirubin, gamma-glutamyl transferase, and creatine kinase to confirm the abnormality and to determine if it is improving or worsening. If the abnormality persists or worsens, clinical and laboratory monitoring must be initiated by the investigator and in consultation with the study medical monitor. Monitoring of ALT, AST, TBL, and ALP must continue until levels normalize or return to approximate baseline levels.

Additional safety data must be collected via the case report form (CRF) if 1 or more of the following conditions occur:

- Elevation of serum ALT to ≥5X ULN on 2 or more consecutive blood tests
- Elevated serum TBL to ≥2X ULN (except for cases of known Gilbert's syndrome)
- Elevation of serum ALP to >2X ULN on 2 or more consecutive blood tests
- Patient discontinued from treatment due to a hepatic event or abnormality of liver tests
- Hepatic event considered to be a SAE

See Appendix 4, for hepatic eCRFs that must be completed for these patients.

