#### **5.13.4. Clinical Laboratory Evaluation**

Laboratory measurements will be analyzed using continuous data (change from baseline) and categorical or ordinal data (proportion of treatment-emergent abnormalities).

If there are multiple records of laboratory measurements at baseline or postbaseline visit, the last record will be used.

Summaries and analyses of continuous data (change from baseline) will be performed using both conventional and International System of Units (SI units).

Change from baseline to each post-baseline visit at which laboratory measurements are taken and change from baseline to the last observation will be summarized and compared between treatment groups using an ANCOVA model. For each lab analyte, the rank-transformation will be applied to the change from baseline for all subjects and all visits prior to analysis. Similarly, an independent rank-transformation will be applied to the baseline values prior to analysis. The model for the fixed effects will include terms for baseline value, treatment and age. This analysis will be done separately for each laboratory analyte.

Treatment differences in the proportion of subjects with treatment-emergent high or treatment-emergent low or treatment-emergent abnormal laboratory values at (1) anytime and (2) each post-baseline visit will be assessed using Fisher's exact test. Treatment-emergent high or low laboratory abnormality will be based on SI unit. For each laboratory analyte, only subjects who were low or normal at baseline and have at least one post-baseline measurement will be included in the denominator when computing the proportion of subject with treatment-emergent high values. Similarly, only subjects who were high or normal at baseline and have at least one post-

baseline measurement will be included in the denominator when computing the proportion of subject with treatment-emergent low values. In addition, treatment differences in the proportion of subjects who were normal at baseline and change to abnormal high or abnormal low values at any post-baseline visit will be summarized.

For urinalysis parameters, baseline to post-baseline shifts will be summarized at each visit. Likelihood ratio chi-square tests will be used to compare increase, no change and decrease shifts in urinalysis parameters between treatment groups at each visit.

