For all laboratory analytes, frequencies of subjects with notable changes (that is, increases or decreases of a prespecified amount unique to each analyte) from baseline to each postbaseline visit were also summarized for all subjects and stratified by low, normal, or high at baseline.

The proportion of subjects with treatment-emergent clinically significant changes from a low value or normal value at all baseline at any time in alanine aminotransferase (ALT), alkaline phosphatase (ALP), and total bilirubin will be summarized by treatment group. Abnormal criteria for treatment-emergent clinically significant changes are presented in [Appendix 2](#). Significant changes of interest for hepatic laboratory values are: ALT  $\geq 3$  x upper limit of normal (ULN), total bilirubin  $\geq 2$  x ULN, alkaline phosphatase (ALP)  $> 2$  x ULN, ALT  $\geq 5$  x ULN, ALT  $\geq 10$  x ULN, and total bilirubin  $\geq 2$  x ULN. Additionally, Hy's Law analysis will be conducted by comparing treatment groups with regard to the proportion of patients with (ALT  $\geq 3$  x ULN OR aspartate aminotransferase (AST)  $\geq 3$  x ULN) AND total bilirubin  $\geq 2$  x ULN. Comparisons between treatment groups will be carried out using Fisher's exact test.

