### **5.13.5. Vital Signs and Other Physical Findings**

Vital sign measurements and weight will be analyzed using continuous data (change from baseline) and categorical data (proportion of potentially clinically significant changes).

If there are multiple records of vital sign or weight measurements at baseline or postbaseline visit, the last record will be used. Summary statistics will be presented for observed values at baseline and for change from baseline results at each scheduled postbaseline visit. Systolic and diastolic blood pressure and pulse (collected in sitting position), orthostatic diastolic and orthostatic systolic blood pressures and orthostatic pulse (measurement after 5 minutes in the supine position minus that after 3 minutes in the standing position), temperature, and weight by treatment group for all subjects in the safety population will be summarized.

With the large number of the scheduled vital sign visits, the MMRM model is not suitable for the change from baseline comparison of treatments due to computational challenge. Change from baseline to each post-baseline visit at which vital signs are taken will be assessed using an ANCOVA model with treatment and as independent factors and baseline value and age as covariates in the model. This analysis will be done separately for each vital sign parameter and weight.

The incidence of treatment-emergent abnormal high or low vital signs and weight will be presented by treatment group and visit. Treatment-emergent vital sign evaluations are defined for evaluations collected after the initiation of study medication. Abnormal criteria for

postbaseline vital signs and weight are presented in [Appendix 3](#). Any vital sign or weight meeting the criteria will be considered abnormal. Treatment differences in the proportion of subjects with treatment-emergent abnormal high or low vital signs and weight will be assessed between treatment groups using Fisher's exact test at (1) any time (2) post-baseline visit.

For each vital sign at each post-baseline visit, only subjects who had a baseline result and had a nonmissing result at that post-baseline visit will be included in the denominator when computing the proportion of subjects with treatment-emergent high, low, or abnormal values.

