### **5.13.6. Electrocardiograms**

Electrocardiogram measurements will be analyzed using continuous data (change from baseline) and categorical data (proportion of treatment-emergent abnormalities).

Since ECG is measured in triplicates, the average of triplicates will be used at baseline and each visit. If there are multiple records after averaging ECG triplicates within a visit, the last record of averages will be used.

The analysis will be done for the following ECG measurements: heart rate, PR, QT, QTc, and RR intervals and QRS duration. All analyses of QTc will be carried out using the Fridericia correction (QTcF) method. These summaries will include data from each visit ECG measures are performed. Change from baseline to each post-baseline visit at which ECG measurements are taken and change from baseline to last observation will be assessed using an ANCOVA model. The model for the fixed effects will include terms for the following independent effects: baseline age, baseline ECG score, and treatment. This analysis will be done separately for each ECG parameter.

Incidence of treatment-emergent abnormal ECGs will be assessed by comparisons at (1) anytime and (2) each post-baseline visit between treatment groups with Fisher's exact test. For analyses of treatment-emergent abnormal ECGs, baseline will be considered as all visits before the initiation of drug dose.

Abnormal ECG criteria and criteria for abnormal QTcF prolongation are presented in [Appendix 1](#).

Treatment-emergent high ECG parameters (heart rate, PR interval, QRS duration, QT and QTcF intervals) are the values which are low or normal at all baseline visits and fall into the high

abnormal categories post-baseline. Similarly, treatment-emergent low ECG parameters (Heart Rate, PR interval, QRS duration) are the values which are high or normal at all baseline visits and fall into the low abnormal categories above.

In addition, treatment differences in the proportion of subjects who have normal baselines with a change to abnormal high or abnormal low values at any post-baseline visits will be summarized.

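### SAP Appendix 2: the SI high limit for haematocrit repeats the percent figures under L/L and can never be met, and the two neutrophil limits are on different bases

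*SAP*

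**What the plan says.** SAP Appendix 2 is headed "Potentially Clinically Significant Laboratory Values". It sets conventional-unit limits and SI limits side by side for each analyte. The two rows at issue read:

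| Analyte | Conventional unit | Low | High | SI unit | Low | High |
|---|---|---|---|---|---|---|
| Haematocrit | % | <30 | >50 (F), >55 (M) | L/L | <0.3 | >50 (F), >55 (M) |
| Neutrophils | cells/mm3 | 1500 | none | "Proportion of 1.0" | ≤0.15 | none |

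Three statements in SAP 5.13.4 bear on how the table might be used:

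- Continuous changes are summarised and analysed in both unit systems.
- For the categorical analysis, "Treatment-emergent high or low laboratory abnormality will be based on SI unit". That paragraph names no appendix.
- A later paragraph says "Abnormal criteria for treatment-emergent clinically significant changes are presented in" Appendix 2. The sentence before it covers only three analytes: "alanine aminotransferase (ALT), alkaline phosphatase (ALP), and total bilirubin will be summarized by treatment group".

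Both haematocrit and segmented neutrophils are collected (protocol Appendix 2, Clinical Laboratory Tests).

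**The concern.** Wherever else a change of unit calls for one, the table converts its limits. A reader will therefore take the two haematocrit columns as the same limits in different units. As printed, the high limits are not the same, and the SI one lies outside the range the quantity can take. If it were programmed as written, the output would show no patient with high haematocrit in any arm. That would look like a reassuring safety result when it is really a consequence of the unit.

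The neutrophil row raises a different question. Its columns hold two different quantities, so the patients flagged as low depend on which column is used. Nothing in the SAP says that two separate criteria are meant.

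**Working it through.** **Inputs.** All limits are from SAP Appendix 2. The white cell limits there, ≤2.8 and ≥15 ×10^9/L, serve as the ends of the range for the neutrophil comparison.

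**Step 1. Control rows.** Dividing the SI limit by the conventional limit gives the factor that the table itself uses.

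- Haemoglobin: 110/11 = 180/18 = 100/10 = 170/17 = 10.
- Albumin: 26/2.6 = 60/6.0 = 10.
- Calcium: 1.875/7.5 = 3/12 = 0.25.
- BUN (one limit only): 10.71/30 = 0.357.
- Glucose: 11/200 = 0.055, and 45.1 × 0.055 = 2.48, as printed.

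In each row with two limits, the same factor serves both.

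**Step 2. Haematocrit.**

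- Low limit: 0.3/30 = 0.01, the correct factor from percent to fraction.
- High limit, women: 50/50 = 1. Men: 55/55 = 1. No conversion was made.
- With the row's own factor: 50 × 0.01 = 0.50 and 55 × 0.01 = 0.55 L/L.
- Printed against converted: 50/0.50 = 55/0.55 = 100.

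The largest possible value in L/L is 1, so a value above 50 or 55 cannot occur. Storing the data differently does not rescue the row. If values labelled L/L were in fact held as percent, the high limits would work, but the low limit of <0.3 would mean below 0.3% and in practice would never be met. Either way, one of the two SI limits is dead.

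**Step 3. Neutrophils.** Absolute count = proportion × white cell count, and 1500 cells/mm3 = 1.5 ×10^9/L. The two limits are equal when the white cell count is 1.5/0.15 = 10 ×10^9/L, and at no other value.

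| White cells (×10^9/L) | 0.15 as a count: 0.15 × WBC × 1000 (cells/mm3) | 1500 cells/mm3 as a proportion: 1.5/WBC |
|---|---|---|
| 2.8 | 420 | 0.536 |
| 5 | 750 | 0.30 |
| 7 | 1050 | 0.214 |
| 10 | 1500 | 0.15 |
| 15 | 2250 | 0.10 |

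Below 10 ×10^9/L the proportion is the harder limit to meet and flags fewer patients. Above 10 it flags more. As an illustration with assumed values, a patient with white cells of 5 ×10^9/L and 20% neutrophils has 0.20 × 5 × 1000 = 1000 cells/mm3. That is below 1500, but 0.20 is not at or below 0.15, so one column flags the patient and the other does not.

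**The case against.** **No output is shown to use these rows.** SAP 5.13.4 refers to Appendix 2 only in the paragraph on ALT, ALP and bilirubin. The treatment-emergent high/low analysis sorts patients as low, normal or high without naming Appendix 2. This stands. A reader might infer that the planned high/low table will certainly report zero high haematocrits. The documents do not support that, because the limits for that table could come from elsewhere, such as laboratory reference ranges. The consequence is conditional on the row being applied.

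**The neutrophil row may not be an error.** The SI cell is openly labelled as a proportion, and no sentence says the columns must be equivalent. This also stands in part. The row is inconsistent with the layout of the rest of the table, but it is not a failed conversion: no single proportion equals 1500 cells/mm3 at all white cell counts. If the SI sentence in 5.13.4 governs Appendix 2, the operative limit is simply ≤0.15 and the conventional cell goes unused. The SAP does not say which was intended.

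**The haematocrit figure may have lost its decimals when the PDF was read.** This cannot be excluded but is unlikely. The decimal in <0.3 survived in the same row, the high-limit text is identical in both columns, and two separate decimals would have to be lost.

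**Other oddities in the table.** The neutrophil figure of 1500 carries no inequality sign, but neither do the SI haemoglobin limits, and the signs may have been lost in reading. A reader might also see an error in the bilirubin and ALP limits, which in the text of 5.13.4 (≥2 and >2 × ULN) differ from those in Appendix 2 (≥1.5 and ≥3 × ULN). The text introduces its list separately as hepatic changes of interest, and it resembles protocol 9.4.6 ("Elevated serum TBL to ≥2X ULN"). It may be a distinct summary, so neither matter is claimed as an error here.

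**Conclusion.** The haematocrit SI high limit is wrong as printed: it is 100 times the converted value and outside the possible range. Confidence in this is high, subject only to the small chance of decimals lost in reading the PDF. The neutrophil row is an inconsistency that needs reconciling. It is not shown to be an arithmetic error, and the documents do not show which limit was meant.

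The severity is minor. The effect reaches only flags for potentially clinically significant laboratory values, and only if these rows are applied: in SI units for haematocrit, and with a choice between columns for neutrophils. The documents give no basis for saying how many patients would be misclassified. The conventional haematocrit column is usable as it stands. Continuous laboratory changes, the primary analysis and all other efficacy analyses are unaffected.

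**What to change.** In SAP Appendix 2:

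- **Haematocrit, SI high limit:** print >0.50 (F) and >0.55 (M) L/L. These are the existing percent limits divided by 100, so no new threshold is introduced.
- **Neutrophils:** put both columns on one basis. If the absolute count is kept, the SI equivalent of 1500 cells/mm3 is 1.5 ×10^9/L. If the proportion is kept, the other column should express the same proportion. The choice is the sponsor's.

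The cost is two table cells, with no new data and no new analysis.

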### Appendix 3. Criteria of Potential Clinical Significant Vital Signs and Weight

Parameter	Unit	Observed Value	And/Or	Change Relative to Baseline	Change from Supine to Standing
Systolic Blood Pressure (supine or sitting)	mmHg	$\geq 180$	And	Increase of $\geq 20$	-
		$\leq 90$	And	Decrease of $\geq 20$	-
Diastolic Blood Pressure (supine or sitting)	mmHg	$\geq 105$	And	Increase of $\geq 15$	-
		$\leq 50$	And	Decrease of $\geq 15$	-
Systolic Blood Pressure (supine to standing)	mmHg	$\leq 80$	And	-	Decrease of $\geq 20$
Pulse (supine or sitting)	bpm	$\geq 120$	And	Increase of $\geq 15$	-
		$\leq 50$	And	Decrease of $\geq 15$	-
Orthostatic hypotension (Systolic)	Decrease in systolic blood pressure when going from 5 minutes supine to 3 minutes standing of $\geq 20$ mm Hg or the inability to stand quickly for the measurements due to symptoms of orthostasis				
Orthostatic hypotension (Diastolic)	Decrease in diastolic blood pressure when going from 5 minutes supine to 3 minutes standing of $\geq 10$ mm Hg or the inability to stand quickly for the measurements due to symptoms of orthostasis				
Orthostatic pulse (Tachycardia)	Increase in heart rate when going from 5 minutes supine to 3 minutes standing of $\geq 30$ bpm				
Weight		Not Applicable		Increase of $\geq 7\%$ Decrease of $\geq 7\%$	

---

## Appendix 4. Complete List of AV-45 (Florbetapir) Parameters

---

SUVr will be obtained for the regions listed below normalized (based on AVID guidelines) and to cerebellar gray matter:

composite summary	lateral temporal cortex left	pons
caudate left	lateral temporal cortex right	putamen right
caudate right	mean cerebellum gray matter	putamen left
cerebellar cortex left	mean whole cerebellum	rectus left
cerebellar cortex right	mesial temporal cortex left	rectus right
cerebellar white matter	mesial temporal cortex right	subcortical white matter
cingulum anterior left	occipital cortex left	temporal cortex left
cingulum anterior right	occipital cortex right	temporal cortex right
cingulum posterior left	orbitofrontal cortex left	thalamus left
cingulum posterior right	orbitofrontal cortex right	thalamus right
frontal cortex left	parietal cortex left	
frontal cortex right	parietal cortex right
